2.1.2. Part JB PF-06873600 Dose Finding in Combination with Endocrine Therapy

After the single-agent PF-06873600 MTDIRDE has been determined for both the IR and MR formulations, enrollment will be initiated into Part JB which will evaluate the PF-06873600 in combination with letrozole and in combination with fulvestrant in independent cohorts in women with HR-positive HER2-negative advanced or mBC. PF-06873600 will be administered orally on a continuous basis (unless the dose schedule has changed during Part JA or Part 1C), while letrozole and fulvestrant will be administered per standard of care.

Available safety and clinical data will be reviewed by the safety review team. The PF-06873600 dose in combination with letrozole may be decreased if determined to not be tolerable. The PF-06873600 dose de-escalation in combination with letrozole will follow the mTPI method. Similarly, the PF-06873600 dose in combination with fulvestrant may be decreased if determined to not be tolerable. The PF-06873600 dose de-escalated in combination with fulvestrant will follow the mTPI method. The MTDIRDE of each of the PF-06873600 formulations (IR and MR) in combination with the respective endocrine therapy (letrozole and fulvestrant) will be declared when at least 6 patients have been enrolled at a dose level that is predicted to be the MTDIRDE for each of the respective combination per the mTPI. Once the MTDIRDE of PF-06873600 in combination with letrozole and the MTDIRDE of PF-06873600 in combination with fulvestrant have been confirmed, a recommended dose for expansion for each combination will be declared and enrollment into Part 2 may be initiated. The decision to dose either the MR or IR or MR and IR formulation in Part 2 will be made following a careful review of all available clinical data and in alignment with C3661001 Safety Team.

Similar to Part JA and/or Part JC, dose escalation, all safety, PK and PD information from safety cohorts in Part JB available will be used to determine the PF-06873600 MTDIRDE for the respective combination treatments.

2.1.3. Part 1C PF-06873600 MR Formulation

A modified release (MR) formulation with two designed release rates shorter duration (eg, 6-hour) and longer duration (eg, 12-hour) release, respectively) has been developed for PF-06873600 and were studied in the Part 1C MR Selection Cohort only. Compared to the Immediate Release (IR) formulation, the MR formulation has the potential to achieve more prolonged effective target inhibition during a dose interval. Emerging pharmacokinetics and safety data for the IR formulation suggest there is a large peak-to-trough fluctuation in steady-state concentrations and a lower maximal concentration (C_{max}) could potentially improve tolerability. Therefore, the MR formulation with the two release rates were evaluated in an MR selection cohort in this study.

The MR selection cohort enrolled 3 to 5 evaluable patients. These patients received two single doses of the MR formulation during a 7-day lead-in period (Day -7 to Day -1), prior to receiving the IR formulation of PF-06873600 twice daily in 28-day cycles. During the 7-day lead-in period, patients will first received a single dose of the shorter release tablets on Day -7, and then another single dose of the longer release tablets on Day-4. The dose for the

shorter and longer release MR tablets to be administered during the lead-in period, as well as the IR dose to be administered starting from Cycle 1 Day 1, were no higher than the highest nominal dose tested found to be safe from the IR dose escalation. Serial PK sampling was performed for 24 hours following each of the MR formulation doses on Day -7 and Day -4, and for 12 hours following the IR formulation morning dose on Cycle 1 Day 1. PK were compared between the shorter and longer release MR tablets, and also between each of the two release rate MR tablets and IR. Based on the PK data from the MR selection cohort, 12-hour release rate provides a slower release compared to the 6-hour release rate, thus achieves more prolonged drug coverage during a dosing interval. Therefore, 12-hour release rate was selected to be further investigated during MR dose escalation.

The MR dose escalation, if to be performed, proceeded with one of the selected MR formulation release rates according to the mTPI method until a MTD is determined. The starting dose for the MR dose escalation was selected to achieve similar steady-state AUC during one dose interval ($AUC_{ss,J}$) as the highest safe IR dose based on prediction. The dose increment will be no more than a 50% increase. After MTD_{IRDE} is determined, a biomarker cohort may be open to enroll patients with HR-positive HER2-negative advanced or mBC requiring mandatory pre- and on-treatment tumor and skin biopsies.

During the Part 1C dose escalation, all available safety information from dose escalation safety and biomarker cohorts in will be used to determine the PF-06873600 MTD_{IRP2D} as a single agent.

The mTPI design uses a Bayesian decision-theoretic framework and a beta/binomial hierarchical model to tailor dose-escalation and de-escalation decisions. These rules are conceptually similar to those used by the 3+3 design and all the dose-escalation decisions for a given trial can be pre-calculated under the mTPI design and presented in a two-way table.

The decision rules to "dose escalate" (E), "no change in dose" (S), "dose de-escalate" (D) or "dose de-escalate, unacceptable toxicity" (U) are described below:

Table 2 Dose Escalation Decision Rules

DLT	n=2	n=3	n=4	n=5	n=6	n=7	n=8	n=9	n=10	n=11	n=12
0	E	E	E	E	E	E	E	E	E	E	E
1	S	S	S	S	E	E	E	E	E	E	E
2	D	D	D	S	S	S	S	S	S	S	E
3		u	u	D	D	S	S	S	S	S	S
4			u	u	u	u	D	S	S	S	S
5				u	u	u	u	u	D	S	S
6					u	u	u	u	u	u	u
7						u	u	u	u	u	u
8							u	u	u	u	u
9								u	u	u	u
10									u	u	u
11										u	u
12											u

Actions to be taken: D = De-escalate the dose; E = Escalate the dose; S = Stay at the dose. U = Unacceptable toxicity.

In principle, all patients must be evaluated for a minimum DLT observation period of 28 days in both Part 1 and Part 2. However, in order to be evaluable for DLT assessment patients need to have received at least 75% of planned doses unless related to treatment emergent toxicity.

The dose escalation in Part 1A and 1C, dose finding in Part 1B, and each arm of the dose expansion in Part 2 of the study will stop as the applicable following criteria are met:

- The maximum sample size has been achieved (approximately 50 patients in Part 1, excluding patients enrolled in biomarker cohorts, and approximately 30 patients in each dose arm in Part 2);
- 6 to 12 evaluable patients (for Parts 1A, Part 1B and Part 1C) that have been enrolled at a PF-06873600 dose level (as a single agent, in combination with letrozole, and in combination with fulvestrant, each) that is predicted to be the MTD per the mTPI method;
- All dose levels explored appear to be overly toxic, and the MTD cannot be determined.

2.1.5. Recommended Dose for Expansion (RDE) and Recommended Phase 2 Dose (RP2D) Definition

The RDE is the dose chosen for further investigation based on Part 1 study results. If the MTD proves to be clinically feasible for long-term administration in a reasonable number of patients, then this dose usually becomes the RP2D. Further experience with the RDE may result in a RP2D dose lower than the RDE. A RP2D for PF-06873600 as a single agent, in combination with letrozole, and in combination with fulvestrant are planned to be individually determined based on the respective RDE/MTD and other considerations including available pharmacodynamic, pharmacodynamic, and clinical benefit data.

2.2. Part 2 PF-06873600 Combination Dose Expansion

Part 2 dose expansion is an open-label, multi-center, non-randomized study to assess the preliminary anti-tumor activity and the safety and tolerability of PF-06873600. PF-06873600 will be administered at the RDE in 28 days cycles in combination with endocrine therapy in two separate dose expansion arms. Patients may be treated with IR or MR formulations depending on emerging data from Part 1 and availability.

2.2.1. Part 2 Respective Starting Doses for PF 06873600 Combination Cohorts

The single agent PF-06873600 RDE from Part 1A will be used to initiate the Part 2 dose expansion arm studies, which may be de-escalated, depending on emerging data if indicated. Additionally, the PF-06873600 RDE in combination with letrozole and PF-06873600 RDE in combination with fulvestrant from Part 1B will be used to initiate the Part 2 respective combination dose expansion arm studies, which may be de-escalated, depending on emerging data if indicated.

2.2.2. Part 2/Arm A PF 06873600 in Combination with Fulvestrant in HR Positive HER2 Negative Locally Advanced or mBC (Second- or Third-Line Setting)

PF-06873600 will be evaluated in combination with fulvestrant at the RDE in HR-positive HER2-negative advanced or mBC in patients who have received prior combined CDK4/6 inhibitor and a nonsteroidal aromatase inhibitor, and up to 1 prior line of chemotherapy in advanced/metastatic setting. This expansion cohort will enroll approximately 40 patients.

2.2.3. Part 2/Arm B -PF 06873600 Part 2/Arm B -PF-06873600 in Combination with Letrozole in HR-Positive HER2-Negative Locally Advanced or mBC (naive to CDK4/6 inhibitors).

PF-06873600 will be evaluated in combination with letrozole at the RDE in HR-positive HER2-negative advanced or mBC in patients, with supportive available preliminary PF-06873600 clinical data. Patients who have not received any prior treatment with a CDK4/6 inhibitor in the advanced or metastatic setting (prior adjuvant therapy with AI is permitted) will be enrolled. This expansion cohort will enroll approximately 30 patients.

2.2.4. Part 2/Arm C-PF-06873600 in Combination with Fulvestrant in HR-Positive HER2-Negative Locally Advanced or mBC (naïve to CDK4/6 inhibitors)

PF-06873600 will be evaluated in combination with fulvestrant at the RDE in HR-positive HER2-negative advanced or mBC in patients who progressed on prior endocrine therapy in advanced/metastatic setting but have not previously received treatment with a CDK4/6 inhibitor in the advanced or metastatic setting. Participants who have prior treatment with CDK4/6 inhibitors, fulvestrant, everolimus, and any agents with MOA that inhibits PI3k mTOR pathway are excluded. This expansion cohort will enroll up to 30 patients.

2.3. Study Objectives and Endpoints

Part IA: Single Agent Dose Escalation and Part JB: Combination Dose Finding	
Primary Objective(s):	Primary Endpoint(s):

Part JA and IC:
 
To assess the safety and tolerability of increasing doses of PF-06873600 in patients with:
 
 • HR-positive HER2-negative advanced or mBC patients (third or fourth line setting). • Locally recurrent/advanced or metastatic TNBC. • Advanced platinum resistant epithelial ovarian cancer/fallopian tube cancer/primary peritoneal cancer • In order to estimate the Maximum Tolerated Dose (MTD) and select the Recommended Dose for Expansion (RDE) for PF-06873600 as a single agent (Part JA and Part I Only). 
Part JB:
 
To assess the safety and tolerability of PF-06873600 at the single agent MTD in combination with letrozole and in combination with fulvestrant (in a de-escalation manner, if indicated) in patients with:
 
 • HR-positive HER2-negative advanced or mBC (third or fourth line setting) in order to establish the MTD and select the RP2D for PF-06873600 in combination with letrozole and in combination with fulvestrant, respectively. 	
Part JA, Part JB and Part JC:
 
 • Dose-Limiting Toxicities (DLTs). • Adverse Events as characterized by type, frequency, severity (as graded by National Cancer Institute Common Terminology Criteria for Adverse Events (NCI CTCAE version 4.03), timing, seriousness, and relationship to study therapy. • Laboratory abnormalities as characterized by type, frequency, severity (as graded by NCI CTCAE version 4.03), and timing. • Vital sign abnormalities. • Heart rate corrected QT interval (eg, QTcF).
Secondary Objective(s):	Secondary Endpoint(s):

 • To evaluate the single- and multiple- dose PK of PF-06873600 when given as a single agent (Part JA and Part IC), in combination with letrozole, and in combination with fulvestrant (Part JB). 	
Pharmacokinetic parameters of PF-06873600
 
 • Single Dose (SD) - C_{max}, T_{max}, AUC_{0-∞} and as data permit, t_{1/2}, AUC₀₋₁₂, C₀, V_{dIF}, and t_{1/2}. • Multiple Dose (MD) (assuming steady state is achieved) - C_{ss,max}, T_{ss,max}, AUC_{ss,r}, C_{ss,min}, CL_{ssIF}, and as data permit, V_{ssIF}, t_{1/2}, and R_{ae}(AUC_{ss,i-r}).

Part IA: Single Agent Dose Escalation and Part JB: Combination Dose Finding	

 To document any preliminary evidence of anti-tumor activity of PF-06873600. 	
 Objective Response (OR), as assessed using the Response Evaluation Criteria in Solid Tumors (RECIST) version 1.1. Time-to-event endpoints: eg, Duration of Response (DOR), Progression-Free Survival (PFS), Time to Progression (ITP).

 To evaluate the pharmacodynamic (PD) markers of CDK pathway modulation following treatment with PF-06873600 in tumor. 	
 Modulation of PD biomarkers (eg, pRb, Ki67) of CDK in tumor.
CCI [REDACTED]	[REDACTED]
[REDACTED]	[REDACTED]
[REDACTED]	[REDACTED]
[REDACTED]	I [REDACTED]
[REDACTED]	I [REDACTED]

Part 2: PF-06873600 Single Agent and Combination Dose Expansion	
Primary Objective(s):	Primary Endpoint(s):

To evaluate the preliminary antitumor activity and confirm the safety and tolerability of PF-06873600:
 
In combination (at the RDE from Part 1B) in patients with:
 
 HR-positive/HER2-negative advanced or mBC {PF-06873600 + fulvestrant} (second or third line setting); HR-positive/HER2-negative advanced or mBC {PF-06873600 + a nonsteroidal aromatase inhibitor} (CDK4/6i naive); HR-positive/HER2-negative advanced or mBC {PF-06873600 + fulvestrant}- (CDK4/6i naive). 	
 Preliminary antitumor activity measure for efficacy includes OR, as assessed using RECIST 1.1. Safety and tolerability: 
 Adverse Events as characterized by type, frequency, severity (as graded by National Cancer Institute Common Terminology. Criteria for Adverse Events (NCI CTCAE v 4.03) timing, seriousness and relationship to study therapy. Lab abnormalities as characterized by type, frequency, severity (as graded by NCI CTCAE v 4.03) and timing. Vital sign abnormalities. Heart rate corrected QT interval (eg, QTcF).

Part 2: PF-06873600 Single Agent and Combination Dose Expansion	
Secondary Objective(s):	Secondary Endpoint(s):

 To farther explore preliminary antitumor activity of PF-06873600. 	
 Time-to-event endpoints: eg, DOR, PFS, overall survival (OS) and TTP.

 To farther evaluate the PK of PF-06873600, in combination with letrozole, and in combination with fulvestrant at the respective RDE. 	Pharmacokinetic parameters of PF-06873600 
 SD - Cmax, Tmax. MD (assuming steady state is achieved) - C_{ss,m,u}, T_{ss,max}, C_{ss,min}, RacCmax,

 To evaluate pharmacodynamic (PD) markers of CDK pathway modulation following treatment with PF-06873600 in combination with fulvestrant or letrozole in tumor. 	
 Modulation of PD biomarkers (eg, pRb, Ki67) of CDK in tumor.
CCI [REDACTED]	[REDACTED]
I [REDACTED]	[REDACTED]
I [REDACTED]	[REDACTED]
I [REDACTED]	[REDACTED]
I [REDACTED]	[REDACTED]

3. INTERIM ANALYSES, FINAL ANALYSES AND UNBLINDING

No formal interim analysis or blinding is planned for this study. The final analysis will be conducted after the last subject last visit (LSLV).

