7. ASSESSMENTS

The collection of the efficacy, safety, PK, biopsy and biomarker data per protocol will be completed as of the primary completion date (PCD). Participants who continue on study beyond PCD will follow local standard of care for safety procedures and the disease assessment. SAE reporting to Pfizer Safety will continue per protocol until end of trial. AEs reporting in eCRF will continue to be collected per local regulatory requirements. Refer to Section 13.2 and [Appendix 8](#) for the details.

Every effort should be made to ensure that the protocol-required tests and procedures are completed as described. However, it is anticipated that from time to time there may be circumstances outside of the control of the investigator that may make it unfeasible to perform the test. In these cases the investigator will take all steps necessary to ensure the safety and well-being of the patient. When a protocol-required test cannot be performed, the investigator will document the reason for this and any corrective and preventive actions that he or she has taken to ensure that normal processes are adhered to as soon as possible. The study team will be informed of these incidents in a timely manner.

For samples being collected and shipped, detailed collection, processing, storage, shipment instructions and contact information will be provided to the investigator site prior to initiation of the study.

See [Appendix 6](#) for alternative measures during public emergencies including the COVID-19 pandemic.

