13. DEFINITION OF END OF TRIAL

13.1. End of Trial in All Participating Countries

End of trial in all participating countries is defined as last subject last visit (LSLV).

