13.2. Primary Completion Date

The Primary Completion Date (PCD) is the date of the last study visit where data is collected for the primary analysis of study outcome(s) also as stated in [Section 13.1](#). The PCD will take place on or around 5 April 2023. The final CSR will include data collected up to PCD. At the time of PCD the applicable participants will either 1) complete the transition to PfizerCares (expanded access) program, where such program is available, or 2) continue on study under Amendment 9 in the countries where expanded access program is not available.

The end of trial will take place when last patient discontinues study treatment or on October 31 2024, whichever occurs first. The study procedures after PCD are detailed in [Appendix 8](#). The supplemental CSR will include safety data collected after PCD until the end of study.

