15. PUBLICATION OF STUDY RESULTS

15.1. Communication of Results by Pfizer

Pfizer fulfills its commitment to publicly disclose clinical trial results through posting the results of studies on www.clinicaltrials.gov (ClinicalTrials.gov), the European Clinical Trials Database (EudraCT), and or www.pfizer.com, and other public registries in accordance with applicable local laws/regulations.

In all cases, study results are reported by Pfizer in an objective, accurate, balanced, and complete manner and are reported regardless of the outcome of the study or the country in which the study was conducted.

www.clinicaltrials.gov

Pfizer posts clinical trial US Basic Results on www.clinicaltrials.gov for Pfizer-sponsored interventional studies (conducted in patients) that evaluate the safety and/or efficacy of a Pfizer product, regardless of the geographical location in which the study is conducted. US Basic Results are submitted for posting within 1 year of the primary completion date (PCD) for studies in adult populations or within 6 months of the PCD for studies in pediatric populations.

PCD is defined as the date that the final patient was examined or received an intervention for the purposes of final collection of data for the primary outcome, whether the clinical study concluded according to the prespecified protocol or was terminated.

EudraCT

Pfizer posts European Union (EU) Basic Results on EudraCT for all Pfizer-sponsored interventional studies that are in scope of EU requirements. EU Basic Results are submitted for posting within 1 year of the PCD for studies in adult populations or within 6 months of the PCD for studies in pediatric populations.

www.pfizer.com

Pfizer posts Public Disclosure Synopses (CSR synopses in which any data that could be used to identify individual patients has been removed) on www.pfizer.com for Pfizer-sponsored interventional studies at the same time the US Basic Results document is posted to www.clinicaltrials.gov.

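### SAP 3 sets one final analysis after LSLV with no data cut-off, while the protocol stops the final CSR at the PCD; AE and exposure summaries and PFS/DOR/TTP censoring dates depend on the choice

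*SAP*

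**What the plan says.** SAP 3 provides for a single analysis: "The final analysis will be conducted after the last subject last visit (LSLV"). The SAP text supplied mentions neither the PCD, a data cut-off nor a supplemental CSR. SAP 1 nevertheless records that version 4.0 (23 March 2023) takes in changes through Protocol Amendment 9 (3 March 2023), the amendment that introduced the PCD and the supplemental CSR.

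The protocol separates the milestones:

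- Protocol 13.1: "End of trial in all participating countries is defined as last subject last visit (LSLV").
- Protocol 13.2: "The Primary Completion Date (PCD) is the date of the last study visit where data is collected for the primary analysis of study outcome(s"), to which the same sentence adds that this is also as Section 13.1 states. Then: "The PCD will take place on or around 5 April 2023".
- Protocol 13.2: "The final CSR will include data collected up to PCD". Safety data from after the PCD go into a supplemental CSR.
- Protocol 13.2: "The end of trial will take place when last patient discontinues study treatment or on October 31 2024, whichever occurs first".
- Protocol 7: "The collection of the efficacy, safety, PK, biopsy and biomarker data per protocol will be completed as of the primary completion date (PCD").

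Under Protocol Appendix 8, no efficacy data need be reported to the sponsor after the PCD, safety assessment follows local standard of care, and AEs and SAEs are still reported. On censoring, SAP 7.1 and the last rows of Tables 6 and 7 censor patients still ongoing at sponsor termination at the date of study termination. No calendar date is given.

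**The concern.** An analyst who follows SAP 3 literally waits for LSLV and, with no cut-off named, uses everything then held. An analyst who follows Protocol 13.2 stops at the PCD. Both would be working from current text.

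Two groups of results depend on the choice. AE summaries (SAP 9.2.3.1) and treatment-administration summaries (SAP 9.2.4) cover all cycles, so a later cut-off adds experience collected on a reduced schedule to experience collected per protocol. PFS, DOR and TTP use a termination date that the reader cannot fix from the SAP. In an open-label study, these choices would then be made with the data in view.

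**Working it through.** No sample size, power or error rate is involved. The check sets the texts side by side and counts days.

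**1. The dates.** Termination decision: 7 September 2022 (Protocol Appendix 8). PCD: about 5 April 2023. Latest end of trial: 31 October 2024 (both Protocol 13.2).

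| Interval | Days | Months (days / 30.4375) |
|---|---|---|
| Decision to PCD | 210 | 6.9 |
| PCD to latest end of trial | 575 | 18.9 |
| Decision to latest end of trial | 210 + 575 = 785 | 25.8 |

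**2. What accrues between the PCD and the end of trial.** The schedule that applies after Amendment 9 has three rows: PF-06873600, fulvestrant and AE reporting. It has no laboratory, ECG or imaging row.

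- *AEs.* SAP 7.2.6 counts events from first dose to 28 days after last dose (or to the day before new anticancer therapy, if sooner). For a patient still on drug, that window extends past the PCD. The number of patients with an event, and each patient's worst grade, can only stay the same or rise as follow-up is added.
- *Exposure.* SAP 9.2.4 summarises time on treatment and cycles started. One patient treated from the PCD to the cap adds 575 / 28 = 20.5 cycles. Protocol 3.1 expects about 6 to 8 cycles per patient.
- *Response, laboratory, ECG.* Per-protocol collection is complete at the PCD, so these data should be essentially the same at either date.

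**3. The censoring date.** A patient alive, on treatment and progression-free at termination meets two rows of Table 6: one censors at the last objective tumour assessment, the other at the termination date. If the second governs, its date has three readings:

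- *7 September 2022 (the decision).* Up to 210 days of per-protocol follow-up before the PCD would fall after the censoring date.
- *PCD.* Censoring falls after the last scan by up to about one scan interval if scans were on schedule (8 weeks, 12 weeks or 4 months, depending on time on study).
- *End of trial.* Censoring falls up to 575 days after the PCD, although no scan after the PCD need reach the sponsor.

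The direction of the last reading is clear. At an event time with d events among n at risk, the Kaplan-Meier factor is 1 − d/n. If c patients remain in the risk set after their last reported scan, it becomes 1 − d/(n + c), which is closer to 1. The curve is raised by patients in whom progression can no longer be recorded. DOR is also to be summarised by mean and maximum (SAP 9.2.2.1), which lengthen directly if censored durations are included.

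**The case against.** **SAP 3 gives timing, not a cut-off.** This is correct. A reader might infer that SAP 3 and Protocol 13.2 state two opposing cut-offs; they do not. SAP 2 says the SAP supplements the protocol, so the PCD limit could be taken to stand. But Protocol 9 lets the SAP modify what the protocol outlines, and a single post-LSLV analysis with no cut-off does not tell the analyst which rule applies.

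**Protocol 13.2 itself ties the PCD to Section 13.1, the LSLV definition.** On that reading the conflict disappears. The same section then dates the end of trial separately and later, so the reading cannot be sustained. It does show that part of the fault is in the protocol.

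**Little is affected.** A reader might infer that response rates and laboratory or ECG results would change. The documents do not support that, because those data are not scheduled or required by the sponsor after the PCD. What remains is AEs, exposure and censoring dates.

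**Late posting of results.** A reader might infer that the SAP forces a breach of the protocol's commitment: "US Basic Results are submitted for posting within 1 year of the primary completion date (PCD) for studies in adult populations". The protocol is consistent here, since both the final CSR and posting run from the PCD. Lateness would require SAP 3 to override Protocol 13.2 and the end of trial to fall after about 5 April 2024; even then it is at most 209 days (6.9 months) to the cap.

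**The termination rule was added deliberately in SAP version 4.0.** It was, so changing SAP 3 alone would leave SAP 7.1 and Tables 6 and 7 in conflict with it. The fix must cover them.

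**Conclusion.** The concern holds in limited form. SAP 3 places the only final analysis after LSLV without a cut-off, although the protocol closes the final CSR at the PCD. The gap is at most 575 days (18.9 months) and may be shorter, because 31 October 2024 is a cap. It matters for AE and exposure summaries and for PFS, DOR and TTP censoring dates, where the three readings span up to 785 days (25.8 months).

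The effect on any estimate cannot be calculated. Only patients in countries without expanded access continue on study, and the documents do not say how many. No hypothesis is tested, so no error rate is at stake. The change is still worth making: it is cheap, and without it the cut-off and censoring date are left to the analyst.

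Assumptions: the PCD falls on 5 April 2023, and the end of trial is taken at its stated cap. Appendix 8 allows 28 to 35 days of follow-up after last dose; a last dose on the cap date would carry follow-up to 28 November to 5 December 2024, which is not counted here.

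**What to change.** 1. **SAP 3.** State that the final analysis uses data up to the PCD, and that safety data after the PCD are summarised separately for the supplemental CSR.
2. **SAP 7.1 and the termination rows of Tables 6 and 7.** Replace censoring at the termination date with censoring at the last adequate tumour assessment on or before the PCD. This agrees with the general rule in SAP 7.1 for progression-free patients and removes the overlap between rows.
3. **Protocol 13.2.** Correct the reference to Section 13.1 in the PCD definition so that the PCD and LSLV are distinct.

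The cost is text edits in these places. No new data or design change is needed. Compared with censoring at the PCD itself, ongoing patients are censored slightly earlier, by up to about one scan interval if scans were on schedule.
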